1.4 Prior Clinical Experience with the Edwards Cardioband System

The Edwards Cardioband System received CE Mark in September 2015. The CE Mark was based on the results of a prospective multicenter clinical trial conducted in Europe. This trial of patients demonstrated the safety and effectiveness of Edwards Cardioband System in mitral annular reduction as a highly effective first-line treatment option for reducing mitral regurgitation (MR) and improving quality of life scores. The Edwards Cardioband System was shown to significantly reduce annular size, with significant improvement in MR acutely, at 6- and 12- months. 23,24 Study patients will be followed for a total duration of years and is currently ongoing with the last patient reaching the follow up in .

Based on the encouraging experience to date, Edwards Lifesciences believes that a multicenter, prospective, randomized pivotal clinical trial for treatment of functional mitral regurgitation is reasonable and warranted.

[figure not shown]
2 Device Description

Edwards Cardioband System ACTIVE Pivotal Clinical Trial PROTOCOL NUMBER: 2017-05

2.1 Edwards Cardioband System Principles of Operation

[figure not shown]
[figure not shown]

Table 2: Edwards Cardioband System Implant Sizes

Refer to the device Instructions for Use for additional device information.

2.2 Device Traceability

Each Edwards Cardioband System component is identified by serial/lot number. The use of the identifiers facilitates full traceability during and after the clinical investigation. A log of all system components shall be maintained for the trial to ensure full traceability for each item delivered, used and/or returned during the course of the clinical investigation.

3 STUDY OBJECTIVE

The objective of this clinical trial is to evaluate the safety and efficacy of the Edwards Cardioband System for transcatheter mitral annular reduction in treating patients with functional mitral regurgitation. Specifically, the transcatheter mitral annular reduction using Edwards Cardioband System plus guideline directed medical therapy (GDMT) will be compared to GDMT alone. The study protocol will ensure consistency in performing the procedure, patient management, and results of the procedure. The results of this study shall be used to support a PMA application for approval of the Edwards Cardioband System when indicated for transcatheter mitral annular reduction to treat functional mitral valve regurgitation.

3.1 Hypothesis

Transcatheter mitral valve repair with the Edwards Cardioband System, combined with guideline directed medical therapy (GDMT), will reduce mitral regurgitation (MR) and improve

MR symptoms and functional capacity in patients with functional MR as compared with GDMT alone.

STUDY DESIGN

This is a prospective, randomized, multicenter clinical evaluation of the Edwards Cardioband System for the treatment of clinically significant functional mitral regurgitation in MR patients who are treated in accordance with current ACC/AHA valve guidelines. 10,11

This investigational plan incorporates a roll-in cohort to provide experience in the use of the Edwards Cardioband System prior to randomizing patients into the pivotal study cohort at a given investigational site. The roll-in cohort will include a maximum of three patients per site (e.g. if 75 sites used, a maximum of 225 roll-in patients). Data for the roll-in patients will be presented and analyzed as a separate cohort. In the event that a roll-in procedure needs to be prematurely terminated prior to full placement of the system, the treating physician may opt to re-attempt the Edwards Cardioband procedure at a later time (typically after 30 days) for this roll-in patient. In such instances, screening and baseline assessments will be repeated as necessary to ensure that they fit within the prescribed timeframes.

This trial randomizes up to 375 eligible patients at up to 75 sites in North America and Europe on a 2:1 randomization ratio to the Edwards Cardioband System + GDMT (Device group) or to GDMT alone (Control group). Primary endpoint data will be available at 30 days (safety) and 1 year (efficacy), and long-term follow-up through 5 years is planned for all patients.

Therefore, it is expected that a maximum of 600 patients will be enrolled (up to 375 pivotal patients plus up to 225 roll-in patients).

A flow chart of the study (Figure 4) is provided on the following page to illustrate the overall design of the trial. Upon confirmation of patient eligibility, confirmatory testing shall be performed and a technical review of the case is performed by the Edwards Clinical support team to assist with device sizing and case planning with the operator(s). The study will utilize a Central Screening Committee (CSC) to evaluate each patient prior to enrollment. Patients shall then be scheduled for the procedure.

Randomization is ideally performed within seven days prior to the scheduled procedure, but no more than 14 days prior. If a patient is randomized to control, the scheduled interventional case is cancelled and the patient is notified that they have been enrolled in the control/medical therapy arm of the trial and will not need to undergo an interventional procedure. The process of randomizing after a case is scheduled has been implemented to ensure that the time frame between randomization and actual treatment is minimized. As depicted in the flowchart, all

patients are followed for 30 days, 6 months, 1 year and annually for a total of 5 years post-index procedure or randomization in the case of the control population.

[figure not shown]

Figure 4: Clinical Study Design Flowchart

5 STUDY ENDPOINTS

5.1 Co-Primary Efficacy Endpoints (evaluated at 1 year)

- Co-primary endpoint I:
 - 1. Prevalence of MR \leq 2+ at one year.
- Co-primary endpoint II:

Hierarchical comparison between the Device and Control groups using Finkelstein-Schoenfeld methodology:

- 1. Time to all cause death
- 2. Number of heart failure hospitalizations
- 3. Improvement in 6 Minute Walk Test (6MWT) vs. baseline (≥ 40 meters improvement)
- Improvement in Kansas City Cardiomyopathy Questionnaire (KCCQ) at one year vs. baseline (≥ 10 points improvement)

The co-primary endpoints will be analyzed in a hierarchical order where the co-primary endpoint I must meet statistical significance in order to proceed to co-primary endpoint II. This approach does not require any adjustment for multiplicity. The co-primary efficacy endpoints were chosen in order to capture the ability of the Edwards Cardioband System to effectively reduce MR (co-primary endpoint I) as well as its ability to improve clinical outcomes through reducing MR (co-primary endpoint II).

5.2 Primary Safety Endpoint (Evaluated through 30 Days post procedure) [Device Group only]

Overall rate of device and procedure related Major Adverse Events (MAEs) through 30 days post-procedure (including death, stroke, myocardial infarction, pericardial effusion requiring drainage, left circumflex coronary artery injury requiring intervention, mitral valve reintervention and access site and vascular complications requiring intervention. The primary safety endpoint was chosen to detect any concerns relating to safety of the Edwards Cardioband System implantation procedure.

5.3 Secondary Safety Endpoints (through 30 Days) [Device Group only]

- 1. Death
- 2. Stroke
- 3. Myocardial infarction
- 4. Pericardial effusion requiring drainage
- 5. Mitral valve reintervention
- 6. Access site and vascular complications requiring intervention
- 7. Left circumflex coronary artery injury requiring intervention
- 8. Need for a new permanent pacemaker

5.4 Secondary Endpoints through 1 Year (Powered):

The following key secondary efficacy endpoints will be tested in comparison to control in a hierarchical order to preserve statistical power.

- 1. MR ≤ 1+
- 2. NYHA Class
- 3. Kansas City Cardiomyopathy Questionnaire (KCCQ)
- 4. 6 Minute Walk Test (6MWT)
- 5. SF-36v2 Health Survey (SF-36)
- 6. Heart Failure Hospitalizations
- 7. Cardiovascular mortality
- 8. All-cause mortality

5.5 Other Secondary Endpoints:

The following outcomes will be assessed for device and control, where appropriate:

For the Device Arm:

1. Device Success (measured at 30 days): Device is deployed as intended and the delivery system is successfully retrieved as intended at the time of the patient's exit from the cardiac catheterization laboratory (per device analysis).

- 2. Procedural Success (measured at 30 days): Device success with evidence of MR reduction ≤ MR2+ at discharge and without the need for a surgical or percutaneous intervention prior to hospital discharge (per patient analysis).
- 3. Clinical Success (measured at 30 days): Procedural success with evidence of MR reduction ≤ MR2+ and without MAEs* at 30 days (per patient analysis).
 - *Major adverse events (MAE) defined as death, stroke, myocardial infarction, pericardial effusion requiring drainage, left circumflex coronary artery injury requiring intervention, mitral valve reintervention and access site and vascular complications requiring intervention.
- 4. Responder analysis percentage of patients who achieve:
 - a. $MR \le 2+$, and
 - b. Meets at least two of the following criteria:
 - Improvement vs. Baseline in Symptoms (e.g., NYHA Class improvement ≥
 - Improvement vs. Baseline in Functional Status (6MWD improvement ≥ 30 ii. meters)
 - Improvement vs. baseline in QoL (KCCQ improvement ≥ 5 points) iii.

For both the Device and Control Arms:

- 1. Patient success (measured at 1 year) is defined as
 - a. Patient remains alive and stroke free, and
 - b. No re-hospitalizations (or equivalents) for HF, and
 - c. Patient meets at least two of the following criteria:
 - i. Improvement vs. Baseline in Symptoms (e.g., NYHA Class improvement ≥ 1)
 - ii. Improvement vs. Baseline in Functional Status (6MWD improvement ≥ 30 meters)
 - iii. Improvement vs. baseline in QoL (KCCQ improvement ≥ 5 points)
- 2. Mean daily steps (measured at 1 year):

Mean daily steps measured during the hours of 6am to 10pm, via an activity monitoring device, during a one month collection period following the 1 year follow-up visit. Patient Success (evaluated at 1 year post index procedure)

5.6 **Echocardiography Parameters (through 5 years)**

Key echocardiography parameters by echo core lab assessment at 30 days, 6 months, yearly at 1-5 years (see Echo protocol for full details):

- 1. MR severity
- 2. LVEDVi
- 3. LVESVi
- 4. TAPSE
- 5. Mitral valve effective orifice area (EOA)
- 6. LV ejection fraction
- 7. Stroke volume
- 8. Left atrial volume
- 9. Tricuspid regurgitation severity
- 10. Estimated pulmonary artery pressure

5.7 **Long-term Outcomes (Through 2,3,4,5 Years)**

- 1. NYHA
- 2. 6 Minute Walk Test (at two years only)
- 3. Heart failure hospitalizations
- 4. Cardiovascular death
- 5. Surgical mitral valve replacement or surgical repair
- 6. Transcatheter based mitral valve interventions
- 7. All-cause mortality
- 8. Cardiac transplantation
- 9. Mechanical hemodynamic support (e.g. LVAD)
- 10. Number of days alive and out of hospital
- 11. NT-proBNP level
- 12. Need for new permanent pacemaker

Quality of Life (assessment with generic and disease specific measures):

- 1. Kansas City Cardiomyopathy Questionnaire (KCCQ)
- 2. SF-36v2 Health Survey (SF-36)

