- (3) If the patient experiences a stroke during the study, Neurological Assessments including NIH Stroke Scale (NIHSS) and Modified Rankin Scale should additionally be performed within 90 days from the date of the stroke by a neurologist, a neurology fellow, or designee.
- (4) Activity monitoring will be collected continuously from baseline to the 6 month visit. At 6 months if compliance is low an additional 1 month of monitoring will be issued. A month of continuous monitoring will be reinitiated at the 1 year follow-up visit
- (5) Economic Data Collection will collect patient billing records for the index procedure.

ABBREVIATIONS

6MWT	6 Minute Walk Test	LVEDVi	Left Ventricular End-Diastolic Volume index
ADE	Adverse Device Effects	LVEF	Left Ventricle Ejection Fraction
ACC	American College of Cardiology	LVESVi	Left Ventricular End-Systolic Volume index
AE	Adverse Event	MAE	Major Adverse Events
АНА	American Heart Association	МІ	Myocardial Infarction
CABG	Coronary Artery Bypass Graft	MR	Mitral Regurgitation
CDS	Edwards Cardioband Delivery System	MRS	Modified Rankin Scale
CEC	Clinical Events Committee	MSAE	Major Serious Adverse Event
CHF	Congestive Heart Failure	NIHSS	National Institutes of Health Stroke Scale
COPD	Chronic obstructive pulmonary disease	NT- proBNP	N-terminal pro b-type natriuretic peptide
CRF	Case Report Form	NYHA	New York Heart Association
CRT	Cardiac Resynchronization Therapy	QOL	Quality of Life
CSC	Central Screening Committee	RO	Radiopaque
СТ	Computerized Tomography	SADE	Serious Adverse Device Effect
DSMB	Data Safety Monitoring Board	SAE	Serious Adverse Event
EF	Ejection Fraction	SAT	Size Adjustment Tool
FDA	Food and Drug Administration	SD	Standard Deviation
GC	Guide Catheter	SF-36	The Short Form (36) Health Survey
GCP	Good Clinical Practice	soc	System Organ Class
GDMT	Guideline Directed Medical Therapy	SOP	Standard Operating Procedure
HF	Heart Failure	TAPSE	Tricuspid annular plane systolic excursion
IC	Implant Catheter	TEE	Transesophageal echocardiography
ICD	Implantable Cardioverter-Defibrillator	TF	Transfemoral
IDS	Implant Delivery System	TMVr	Transcatheter Mitral Valve Repair
ISO	International Standardization Organization	TSS	Transseptal Steerable Sheath
KCCQ	Kansas City Cardiomyopathy Questionnaire	TTE	Transthoracic Echocardiography
LVEDD	Left Ventricle End-Diastolic Dimension		

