6.6 Screening / Baseline (Pre-Randomization)

Patients who are considered qualified for potential study eligibility will undergo assessments by the local Heart Team as outlined below after signing the appropriate consent form (screening and/or study consent).

- Informed Consent Form (screening and/or study consent)
- Medical History
- NYHA Class
- STS Score
- Cardiovascular Medications assessment
- Modified Rankin score

PROTOCOL NUMBER: 2017-05

- Targeted physical examination
- 12-lead ECG
 - The baseline rhythm will be documented if patients have atrial rhythm (sinus, paroxysmal atrial fibrillation (AF), persistent AF, long-standing AF, and/or permanent AF)
- Transthoracic echocardiogram (TTE); (performed in accordance with core lab imaging acquisition protocol)
- Transesophageal echocardiography (TEE); (performed in accordance with core lab imaging acquisition protocol)
- Cardiac CT Imaging (performed in accordance with core lab imaging acquisition protocol)
- Pregnancy Test (for female patients of child bearing potential)
- Coagulation Panel (PT, PTT; INR for patients on Vitamin-K antagonist)
- Complete Blood Count (WBC with differential, RBC, HCT, Hgb, platelet count)
- Chemistry Panel (BUN, CO₂, Creatinine, Glucose, Cl, K, Na, AST (GOT), ALT (GPT), GGT, serum Total Protein, Albumin, Total Cholesterol, HDL Cholesterol, Uric Acid)
- NT-Pro-BNP or BNP
- Kansas City Cardiomyopathy Questionnaire (KCCQ)
- SF-36v2 Health Survey (SF-36)
- 6 Minute Walk Test (6MWT)
- Adverse Events (adverse events will be collected from the time patient signs informed consent until they complete or exit the study)
- Canadian Study of Health and Aging (CSHA) Clinical Frailty Scale[©]
- Patient Preference Survey
- Activity Monitoring initiation with daily data collection through the 180 day follow-up visit.² Patients may opt out of activity monitoring during the informed consent process or at any time after by notifying the investigator.

² Activity Monitoring components to be implemented at system launch. Patients enrolled prior to system launch will not be required to participate in these assessments.

PROTOCOL NUMBER: 2017-05

Cardiac CT

- Patients will be asked to wear the device as much as possible as waking and sleep activity data will be collected. Daily compliance tracking will be measured as a minimum of 8 hours activity data collection between 6am to 10pm.

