Patients with a documented intolerance to Guideline Directed Medical Therapy (GDMT) will be eligible for study inclusion. All patients (i.e. whether assigned to Device and Control groups) shall continue to receive stable Guideline Directed Medical Therapy as directed by current heart failure guidelines (including use of cardiac resynchronization therapy, as indicated).^{27,28} This implies that the GDMT regimen in principle remains unchanged until primary efficacy endpoint, unless medically warranted. Changes to GDMT (doubling or halving of dose) will be documented including whether these occurred due to improvement, deterioration, or no change in the patient's condition. Medical management should continue under the direction of a heart failure specialist at regular intervals according to current heart failure guidelines.^{27,28}

FOLLOW-UP EVALUATIONS

Follow-up evaluations will be scheduled for 30 days, 180 days, 1 year, 2 years, 3 years, 4 years, and 5 years.

- For patients assigned to the Device group, the follow-up visits are scheduled based on the date of the Edwards Cardioband System index procedure.
- For patients assigned to the Control group, the follow-up visits are scheduled based on the date of randomization.
- Note: A patient in the Control group may be offered an opportunity to receive an Edwards Cardioband System after they have been followed for a minimum of 1 year and completed their primary efficacy endpoint assessment. At the time of their 1 year follow-up visit, if the patient chooses to receive the investigational device, they will be evaluated in accordance with the eligibility criteria (including concurrence by the site Heart Team and the CSC). If the patient is still eligible for enrollment, he/she will be offered an opportunity to receive the device. If the patient receives the Edwards Cardioband System implant, he/she shall be followed in accordance with the clinical

protocol schedule or at a minimum for two years if the product has received PMA Approval. This group shall be summarized as a separate cohort.

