9.2 One Hundred Eighty (180) Day Follow-Up Evaluation

An evaluation will be scheduled for 180 day follow-up (± 14 days). The following assessments will be performed:

- Medical History
- NYHA Class
- Cardiovascular Medications
- Targeted Physical Exam
- 12-lead ECG
- Transthoracic Echocardiography
- Complete blood count (no WBC differential necessary)
- Chemistry panel
- NT-Pro-BNP or BNP
- Kansas City Cardiomyopathy Questionnaire (KCCQ)
- SF-36v2 Health Survey (SF-36)
- 6 Minute Walk Test (6MWT)
- Neurological Assessments

Neurological Assessments will be conducted by a neurologist, a neurology fellow, or designee. Every effort should be made to have a neurologist or neurology fellow perform the neurological assessments, or alternatively, a trained research team member certified in stroke assessments, which consist of:

- NIHSS
- Modified Rankin Scale (mRS): mRS can be obtained by a certified research team member via phone interview with the patient or caregiver member if the patient is unable to visit the research office.
- Continued Activity Monitoring data collection from baseline to the 180 day follow-up.
 - At the 180 day follow-up visit, the patient will return the Activity Monitoring Devices.
 If a patient's daily wear compliance rate (minimum 8 hours between 6am to 10pm) is
 less than 50% in the 30 days prior to the visit, an additional month (30 days) of Activity
 Monitoring will be completed. Devices will be returned following the month of Activity
 Monitoring.
- Adverse Events

PROTOCOL NUMBER: 2017-05

If the patient reports any adverse events that are potentially serious during the follow-up period, the patient should return to the investigator's facility for further evaluation of the event.

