9.3 One (1) Year Follow-Up Evaluation

An evaluation will be scheduled for the 1 year follow-up (± 45 days). The following assessments will be performed:

- Medical History
- NYHA Class
- Cardiovascular Medications
- Targeted Physical Exam
- 12-lead ECG
- Transthoracic Echocardiography
- CBC (no WBC differential necessary)
- Chemistry panel
- NT-Pro-BNP or BNP
- Kansas City Cardiomyopathy Questionnaire (KCCQ)
- SF-36v2 Health Survey (SF-36)
- 6 Minute Walk Test (6MWT)
- Adverse Events

If the patient reports any adverse events that are potentially serious during the follow-up period, the patient should return to the investigator's facility for further evaluation of the event.

Neurological Assessments

PROTOCOL NUMBER: 2017-05

Neurological Assessments will be conducted by a neurologist, a neurology fellow, or designee. Every effort should be made to have a neurologist or neurology fellow perform the neurological assessments, or alternatively, a trained research team member certified in stroke assessment, which consist of:

- NIHSS
- Modified Rankin Scale (mRS): mRS can be obtained by a certified research team member via phone interview with the patient or caregiver member if the patient is unable to visit the research office.
- Activity Monitoring data collection will be restarted at the time of the 1 year visit. The
 patient will be provided Activity Monitoring devices and following a month (30 days) of
 data collection will be instructed to return the device.

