### 3.7 Other Secondary Endpoints

The following outcomes will be assessed between Device and Control, where appropriate:

For the Device Arm:

1. Device Success (measured at 30 days): Device is deployed as intended and the delivery system is successfully retrieved as intended at the time of the patient's exit from the cardiac catheterization laboratory (per device analysis).

THIS DOCUMENT CONTAINS CONFIDENTIAL AND PROPRIETARY INFORMATION OF EDWARDS LIFESCIENCES, LLC. IT MUST NOT BE REPRODUCED OR DISCLOSED TO THIRD PARTIES WITHOUT PRIOR WRITTEN PERMISSION OF EDWARDS LIFESCIENCES, LLC. (This template is required by ))

	2017-05 Sta	tistical Analysis Plan		8	1.0   7/16/20	19
E	Revision Date: Febr	uary 28, 2019	Rev		For Use Only by Affiliates of Edwards Lifesciences	Page 7 of 18
Edwards	Title	Statistical Analysis Plan	for	ACTIVE	2017-05	

2. Procedural Success (measured at 30 days): Device success with evidence of MR reduction  $\leq$  2+ at discharge and without the need for a surgical or percutaneous intervention prior to hospital discharge (per patient analysis).

3. Clinical Success (measured at 30 days): Procedural success with evidence of MR reduction  $\leq$  2+ and without MAEs\* at 30 days (per patient analysis).

\*Major adverse events (MAE) defined as death, stroke, myocardial infarction, pericardial effusion requiring drainage, left circumflex coronary artery injury requiring intervention, mitral valve reintervention and access site and vascular complications requiring intervention.

4. Responder analysis percentage of patients who achieve:

- a. MR  $\leq$  2+ and
- b. Meets at least two of the following criteria:
  - i. Improvement vs. baseline in symptoms (e.g., NYHA Class improvement  $\geq$  1)
  - ii. Improvement vs. baseline in functional status (6MWT improvement ≥ 30 meters)
  - iii. Improvement vs. baseline in QoL (KCCQ improvement ≥ 5 points)

For both the Device and Control Arms:

- 1. Patient success (measured at 1 year) is defined as
  - a. Patient remains alive and stroke free,
  - b. No re-hospitalizations (or equivalents) for HF, and
  - c. Patient meets at least two of the following criteria:

i. Improvement vs. baseline in symptoms (e.g., NYHA Class improvement  $\ge 1$ ) ii. Improvement vs. baseline in functional status (6MWD improvement  $\ge 30$  meters) iii. Improvement vs. baseline in QoL (KCCQ improvement  $\ge 5$  points)

2. Mean daily steps (measured at 1 year):

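### One-year mean daily steps has no wear-time rule and no baseline adjustment, although the protocol already holds a compliant-day definition, a repeat-month rule and baseline steps

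*Protocol*

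**What the plan says.** Protocol 5.5 (Other Secondary Endpoints, both arms) and SAP 3.7 word the endpoint identically: "Mean daily steps measured during the hours of 6am to 10pm, via an activity monitoring device, during a one month collection period following" the 1-year visit. Nothing is added on valid days, minimum number of days, unworn hours or baseline.

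The missing pieces exist elsewhere in the protocol, for other purposes:

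- **Compliant day (6.6).** "Daily compliance tracking will be measured as a minimum of 8 hours activity data collection between 6am to 10pm". The window is 16 hours long, so the threshold is half of it.
- **Repeat month (9.2).** If the daily compliance rate is "less than 50% in the 30 days prior to the visit, an additional month (30 days) of Activity" Monitoring follows. Footnote 4 of the visit schedule (Tables 1 and 4) ties this to one visit: "At 6 months if compliance is low an additional 1 month of monitoring will be issued".
- **One-year collection (9.3).** The "patient will be provided Activity Monitoring devices and following a month (30 days) of" data collection returns the device. No compliance threshold or repeat is given.
- **Baseline (6.6).** "Activity Monitoring initiation with daily data collection through the 180 day follow-up visit". Patients may opt out, and those enrolled before the system's launch need not take part.
- **Analysis.** Protocol 13.4.5 makes the additional secondary endpoints descriptive and defers detail to the SAP. SAP 8.5 lists technical, device, procedural and patient success and the responder analysis, but not steps.
- **Control option (section 9).** "At the time of their 1 year follow-up visit, if the patient chooses to receive the investigational device, they will be" assessed again for eligibility, with Heart Team and screening committee concurrence.

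**The concern.** Steps are the trial's only device-recorded measure of daily-life activity. A watch that is not worn records no steps, so a mean that includes unworn or barely worn days mixes activity with wear. Control patients are told their assignment (Protocol section 4), so wear may differ by arm, and it may also depend on how ill or motivated a patient is. The protocol treats low wear as a problem at 180 days but leaves unprotected the only month that feeds the endpoint.

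As written, whoever programs the endpoint must choose a day rule that no document sets. The plan also collects pre-randomisation steps and assigns them no role in the arm comparison, which gives up precision already paid for.

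**Working it through.** The documents give no SD, effect, power or sample size for steps, so there is no plan figure to reproduce. The check has four parts.

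**1. Does any text supply the rule?**

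| Element | Where it exists | Applied to 1-year steps? |
|---|---|---|
| Compliant day, at least 8 of 16 h | Protocol 6.6, 9.2 | Not in Protocol 5.5 or 9.3, nor SAP 3.7 |
| Repeat month if under 50% | Protocol 9.2, schedule footnote 4 | Not in 9.3 |
| Baseline steps | Collected under 6.6 | No analysis names them |
| Analysis method | 13.4.5 defers to SAP | SAP 8.5 omits steps |

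SAP 6.1 offers change from baseline for unnamed selected endpoints. SAP 6.2 says no imputation and is silent on partly worn days. The gap is real.

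**2. Wear artefact (assumed wear patterns, equal true activity).** Let a share p0 of days be unworn and p1 be short (uniform 0 to 8 h, mean 4), with the rest full (uniform 10 to 16 h, mean 13). Steps accrue in proportion to worn hours. Mean recorded hours = 4·p1 + 13·(1 − p0 − p1).

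- Device, p0 = 5%, p1 = 10%: 0.40 + 11.05 = 11.45 h
- Control A, 15% and 15%: 0.60 + 9.10 = 9.70 h
- Control B, 25% and 20%: 0.80 + 7.15 = 7.95 h

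| Days averaged | Device vs Control A | Device vs Control B |
|---|---|---|
| All 30 | 11.45/9.70 − 1 = 18.0% | 11.45/7.95 − 1 = 44.0% |
| Any wear | (11.45/0.95)/(9.70/0.85) − 1 = 5.6% | (11.45/0.95)/(7.95/0.75) − 1 = 13.7% |
| At least 8 h | 13/13 − 1 = 0% | 13/13 − 1 = 0% |

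A patient-level simulation of 30 days agrees: 18.2%, 5.8% and 0.2% against Control A; 43.3%, 13.0% and −0.5% against Control B. With the same wear pattern in both arms the difference is nil.

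Two limits apply. The 8-hour rule works completely here because full days were given the same wear in both arms. If full days differ, the artefact passes through: 11 vs 12 h gives 1 − 11/12 = 8.3%, and 10 vs 12 h gives 1 − 10/12 = 16.7%, and all those days satisfy the rule. Also, in the Control B pattern 23% of Control patients have under 50% compliant days and no Device patients do, so dropping low-wear patients could itself unbalance the arms.

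**3. Baseline adjustment (assumed correlation r).** SE = SD·√(1/nC + 1/nD)·√(1 − r²). The detectable difference at 80% power and two-sided 0.05 is (1.960 + 0.842)·SE, used only as a scale. N = 300 is the plan's evaluable number for co-primary II. N = 225 is 60% of 375, its data-availability assumption for co-primary I (Protocol 13.5). Allocation is 2:1.

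| r | Variance cut, r² | Sample equivalent, 1/(1 − r²) | SE and detectable difference, N = 300 | Same, N = 225 |
|---|---|---|---|---|
| 0 | 0 | 1.00 | 0.122 and 0.343 SD | 0.141 and 0.396 SD |
| 0.5 | 25% | 1.33 | 0.106 and 0.297 SD | 0.122 and 0.343 SD |
| 0.7 | 49% | 1.96 | 0.087 and 0.245 SD | 0.101 and 0.283 SD |

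A plain change score has SE factor √(2 − 2r), which equals 1 at r = 0.5, so it helps only above that.

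If a fraction f lacks baseline steps, complete-case ANCOVA is worth (1 − f)/(1 − r²). At f = 25% and r = 0.5 that is 0.75 × 1.33 = 1.00, and the gain has gone. Keeping those patients through a missing-baseline indicator gives about 1/(1 − (1 − f)·r²) = 1/(1 − 0.75 × 0.25) = 1.23. At r = 0.7 the two figures are 0.75 × 1.96 = 1.47 and 1/(1 − 0.75 × 0.49) = 1.58.

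**4. Overlap with Control implants.** The 1-year window is days 320 to 410 (SAP 5.2). A 30-day collection begun by day 335 ends by day 365, before section 9 permits a Control implant. A repeat month would run to at least day 320 + 60 = 380.

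**The case against.** The best reply is that this is an untested descriptive endpoint, that SAP 6.1 leaves room for change-from-baseline summaries and covariate analyses, and that a day-level rule could be set at programming. The first part stands and limits the importance of the point. The second does not close the gap, because steps are not named there. The third leaves a choice that affects the result to be made without a written rule.

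The remedies also have costs. An 8-hour rule leaves differences within 8 to 16 h untouched, excluding low-wear patients can select by illness, complete-case ANCOVA can lose its gain, and a repeat month moves Control collection into the period when implants are allowed. All of this stands, and it shapes the fix.

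Several stronger readings are tempting, and the documents do not support them:

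- A reader might infer that the plan instructs every day to count whatever the wear. It does not say so; the rule is simply absent.
- A reader might infer that the step comparison is biased. That needs wear to differ by arm, which no document quantifies.
- A reader might take steps as the only continuous functional measure. Six-minute walk distance is also analysed as continuous, as a tested key secondary endpoint (Protocol 13.4.4, SAP 8.4).
- A reader might infer that Control steps are contaminated by later implants. Section 9 requires at least one year, a completed primary assessment and renewed eligibility review, and 9.2.1 advises visits early in the window. Overlap within 30 days is possible but unlikely.

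**Conclusion.** The concern holds as a gap in specification. The one-year step endpoint has no valid-day or minimum-wear condition, no low-wear rule for its own collection month, no use of baseline and no named analysis in SAP 8.5.

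The size rests on assumptions. With equal true activity, the spurious difference is about 18% or 44% under the two uneven wear patterns if all days count, and zero if wear is equal. Baseline adjustment would cut variance by 25% to 49% at a correlation of 0.5 to 0.7, worth 1.33 to 1.96 times the sample with complete baselines. No alpha, power or primary-endpoint statement is affected. This is an inexpensive improvement to a supporting endpoint and does not threaten the trial's main conclusions.

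**What to change.** Amend Protocol 5.5 and 9.3 and SAP 3.7 and 8.5, before unblinding:

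1. **Baseline.** Estimate the arm difference in 1-year mean daily steps by ANCOVA on pre-randomisation mean daily steps. Define the baseline window so that it ends before randomisation. Keep patients with 1-year steps but no baseline (for example, enrolled before system launch) through a missing-baseline indicator.
2. **Wear.** Average over days with at least 8 h of data between 6am and 10pm, and state the minimum number of such days (the existing 50% figure would be 15 of 30). Report wear time by arm. Add one sensitivity analysis adjusted for wear time, or using steps per worn hour, and another that keeps low-wear patients.
3. **Repeat month.** Apply the existing 180-day rule to the 1-year month.
4. **Minor safeguard.** Exclude Control step days after any post-1-year Cardioband implant. This matters a little more once a repeat month is allowed.

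The cost is protocol and SAP wording, one site instruction, a repeated month for a few patients and some extra analysis. The device and data stream already exist.
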